2. OBJECTIVES

2.1 Primary Objective:

To compare the volume and intensity of physical activity 15 years after surgery in patients after hip resurfacing and total hip replacement.

2.2 Secondary Objective(s):

To explore the association between the participants' physical activity and functional outcome scores.

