4. STUDY POPULATION

We will only approach patients that have participated in a previous randomised controlled trial (34) that was conducted in Rijnstate hospital between 2007-2008. These include 34 patients after hip resurfacing and 26 patients after total hip replacement.

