8.2 Randomisation, blinding and treatment allocation

In this observational (follow-up) study participants will not be randomised, blinded or treated. The potential participants for this current study have previously participated in a randomised controlled trial. In this RCT (34), a total of 82 patients were randomly assigned to receive resurfacing hip arthroplasty (RHA, $n = 34$) with a 6-mm thick cobalt-chromium cup or conventional total hip arthroplasty (THA, $n = 26$) with a more conical threaded titanium cup. All participants of this previous RCT will be contacted to ask if they are willing to participate in this follow-up study.

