10. STATISTICAL ANALYSIS

10.1 Primary study parameter(s)

Following the devices' return to the researcher, the recorded data will be downloaded and stored securely in a dedicated study folder on Rijnstate's digital network. The raw triaxial wrist and thigh acceleration data will be auto-calibrated to local gravitational acceleration (in g) and then converted to a Vector Magnitude (VM). VM, or Euclidean Norm, can be interpreted as the magnitude of acceleration the device was subjected to at each measurement, including gravitational acceleration. Non-wear detection procedures will be applied, and any such non-wear periods will be excluded from these analyses. The acceleration signal will be summarised to a common time resolution of one observation per minute and subjected to prediction models

to calculate physical activity energy expenditure, time in moderate-to-vigorous physical activity, and step count.

Raw accelerometry data will be processed using the R-project for Statistical Computing and open-source packages (R Foundation for Statistical Computing, Vienna, Austria). Statistical analysis will be conducted using STATA/SE version 17 (StataCorp, College Station, TX, USA). For descriptive statistics, we will report medians (interquartile ranges) or means (standard deviations) for continuous variables and proportions for categorical variables. To examine face validity and the performance of each multi-level linear regression model, we will conduct ANOVA repeat measures analysis to calculate Pearson's coefficient and Root Mean Squared Error metrics. Differential bias will be assessed by age, sex, and BMI categories.

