10.2 Secondary study parameter(s)

Descriptive analysis of participant demographics and outcomes will be conducted. Medians and interquartile ranges will be calculated for discrete data, such as scores from the questionnaires (IPAQ-SF, SQUASH, EQ-5D-5L, and OHS). These will be visualised through box plots. Mean and standard deviation will be calculated for continuous parameters.

To conduct aetiological analysis based on sample size, we will perform univariate and multivariate regression to assess for statistically significant confounders in relation to the questionnaire outcomes, such as PAEE and patient characteristics.

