12. ADMINISTRATIVE ASPECTS, MONITORING AND PUBLICATION

12.1 Handling and storage of data and documents

All data handling and storage will comply with the EU General Data Protection Regulation and the Dutch Act on Implementation of the General Data Protection Regulation (Dutch: Uitvoeringswet AVG). All data collected during this study will be managed according to the FAIR principles in order to enhance and improve Findability, Accessibility, Interoperability and Reuse of research data.

All patient data will be handled confidentially. Each subject will be given an identification code and only the investigators involved in this study will have access to the subject identification code list which can be used to link the data to the patient. The code list and all raw patient data will be stored in a designated research folder on Rijnstate's local computer mainframe.

The Rijnstate coordinating investigator/project leader will collect the patient source data from the electronic patient records. These data comprise the participant's hospital identification number, age, gender, Body Mass Index (BMI), the presence and severity of any cardiovascular, pulmonary or neuromuscular diagnoses, and the use of medications for these diagnoses. After full data collection, data will be transferred to STATA/SE version 17 (StataCorp, College Station, TX, USA). In this spreadsheet the participant data will be non-identifiable/anonymous. All accelerometer and patient-related (questionnaire) data will be coded and securely shared with the UK investigators via Surf Filesender (<https://www.surf.nl/en/services/surffilesender>). All data collected during this study will be kept under secure conditions at Rijnstate Hospital for 15 years after the research has ended and then it will be destroyed. Any information collected will be treated as confidential and used only in this study unless otherwise specified. All source data relating to consented study participants will be stored and processed in line with Rijnstate Hospital requirements. All source data held in paper form (Informed Consents) will be scanned and securely stored as soon as possible after the participant has signed it. Paper copies will be stored in the secured research lockable cabinet at the department of Orthopaedics of Rijnstate.

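### Section 10.1 specifies no resurfacing-versus-total-hip estimate for the activity endpoints; followed as written the comparison is crude, although age and sex are collected and could be prespecified as covariates

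*Combined protocol and SAP*

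**What the plan says.** Section 2.1 sets the primary objective: "To compare the volume and intensity of physical activity 15 years after surgery in patients after hip resurfacing and total hip replacement". Section 8.1.1 names the main endpoints as PAEE and its intensity distribution, from both devices, and step count from the wrist device.

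Section 10.1, which covers these endpoints, contains three analysis statements after the signal processing:

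- A descriptive one: "For descriptive statistics, we will report medians (interquartile ranges) or means (standard deviations) for continuous variables and proportions for categorical variables".
- A reference to multi-level linear regression models, made only to say how their face validity and performance will be examined (a correlation coefficient and root mean squared error). Outcome, group term and covariates are not given.
- A check of differential bias across categories of age, sex and BMI.

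Section 10.2 plans regressions to look for statistically significant confounders "in relation to the questionnaire outcomes, such as PAEE and patient characteristics".

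Section 12.1 lists what is taken from the patient records: "These data comprise the participant's hospital identification number, age, gender, Body Mass Index (BMI", followed by cardiovascular, pulmonary and neuromuscular diagnoses and the medication for them.

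On who is compared, section 4 says "These include 34 patients after hip resurfacing and 26 patients after total hip replacement", and section 8.2 says "In this observational (follow-up) study participants will not be randomised, blinded or treated".

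**The concern.** The one comparison the study exists to make has no stated estimator. If 10.1 is followed literally, the reader gets a summary per implant group, and any difference drawn from it is unadjusted. Two things are then at stake.

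The first is precision. The groups are small, and whatever variation in activity age and sex explain stays in the error term.

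The second is comparability. The groups were formed by randomisation in the earlier trial, but those analysed here are the people who are alive, can be reached and consent about 15 years later. If that selection works differently in the two groups, age and sex may differ systematically. Both variables are in hand, and neither can be altered by the implant.

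**Working it through.** **Where age and sex enter the plan**

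| Place | Use | An RHA-THA contrast in activity? |
|---|---|---|
| 10.1, descriptive statistics | none stated | no estimate named |
| 10.1, multi-level model | covariates not stated | not stated |
| 10.1, differential bias | categories of age, sex, BMI | no; it follows the model-performance metrics |
| 10.2, regressions | patient characteristics | no; tied to the questionnaire outcomes |

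No section puts age or sex into an implant contrast for PAEE, intensity or step count, and no section rules it out.

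**Inputs.** Group sizes 34 and 26 come from section 4. The documents give no SD, effect size, alpha, power or expected uptake, so there is no planned figure to reproduce and everything below is in SD units. Assumed: R², the share of between-person variance explained by age and sex, 0.15-0.35, with 0.05-0.10 as a pessimistic case; uptake of 100%, or 60% (34 × 0.6 ≈ 20 and 26 × 0.6 ≈ 16).

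**Crude standard error.** SE = √(1/n₁ + 1/n₂).

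- 34 v 26: √(0.02941 + 0.03846) = 0.261 SD. With t on 58 df (2.002), the 95% half-width is 0.52 SD.
- 20 v 16: √(0.05 + 0.0625) = 0.335 SD.

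**Adjusted standard error**, including the expected cost of estimating k = 2 covariates: SE × √[(1 − R²)(1 + k/(N − k − 3))].

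- N = 60: penalty 1 + 2/55 = 1.0364.
- N = 36: penalty 1 + 2/31 = 1.0645.

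The equivalent sample multiplier is 1/[(1 − R²) × penalty].

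| Groups | R² | (1 − R²) × penalty | Adjusted SE | Sample multiplier |
|---|---|---|---|---|
| 34 v 26 | 0.15 | 0.8809 | 0.245 | 1.14 |
| 34 v 26 | 0.35 | 0.6736 | 0.214 | 1.48 |
| 20 v 16 | 0.15 | 0.9048 | 0.319 | 1.11 |
| 20 v 16 | 0.35 | 0.6919 | 0.279 | 1.45 |
| 20 v 16 | 0.10 | 0.9581 | 0.328 | 1.04 |
| 20 v 16 | 0.05 | 1.0113 | 0.337 | 0.99 |

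At 34 v 26 the 95% half-width becomes 2.003 × 0.245 = 0.49 SD to 2.003 × 0.214 = 0.43 SD (56 df).

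**Imbalance.** A covariate gap of g SD, with correlation r between covariate and activity, shifts the crude contrast by r × g. If selection left an age gap of 0.25-0.5 SD and r is 0.3-0.5 (all assumed), the shift is 0.3 × 0.25 = 0.075 SD to 0.5 × 0.5 = 0.25 SD. A gap of up to 1.96 × 0.261 = 0.51 SD can arise by chance alone at 34 v 26, but chance gaps are already reflected in the crude SE. The shift therefore counts as additional bias only where the gap is systematic.

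**The case against.** **The multi-level model may be the adjusted comparison.** It stands under the primary parameters and its covariates are unstated, so a reader who infers that the plan excludes age and sex goes too far. The documents support only that their entry is not specified. An undefined model mentioned for its performance is still not a prespecified contrast.

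**The groups were randomised.** Under randomisation the crude difference is unbiased on average. It would be wrong to count chance imbalance once as bias and again as lost precision. That stands. What randomisation does not cover is selection since then. Section 8.2 states that "a total of 82 patients were randomly assigned to receive resurfacing hip arthroplasty" or THA, yet the arms it gives sum to 34 + 26 = 60, leaving 22 unexplained. A reader might infer that these 22 were lost selectively and that the comparison is biased. The documents say neither, and give no direction or size. The figures need reconciling; they show that selection is possible, not that it happened.

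**Section 10.2 already handles confounding.** Its wording is loose and names PAEE, but the likelier reading has PAEE as an explanatory variable for questionnaire scores. It also picks confounders by significance, which in about 60 people can miss a relevant imbalance and leaves the choice until after the data are seen.

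**The aim is exploratory and the gain modest.** Section 1.3 speaks of exploring whether activity varies, and no test or power is claimed. This limits the urgency. It does not remove the need to say how the primary difference will be estimated.

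**Conclusion.** The point holds in this form: section 10.1 does not specify an RHA-THA estimate for the activity endpoints, and followed as written it gives a crude comparison even though age and sex are collected. It should be corrected before the data are analysed.

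The size is moderate and illustrative. At 34 v 26, adjustment cuts the SE by 6% (R² 0.15) to 18% (R² 0.35). At 20 v 16 with R² of 0.05-0.10, it ranges from a trivial loss to a 2% smaller SE. These figures rest on assumed R² and uptake, and on 34 and 26 being the ceiling for the two groups.

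Any bias would come from selective survival or uptake. Its presence, direction and size cannot be taken from the documents, and adjustment for age and sex would remove only the part that runs through those two variables.

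**What to change.** Add to section 10.1:

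- **Endpoints.** PAEE, one named intensity summary (for example MVPA time, or the MVPA share of PAEE) and step count, with the device stated for each.
- **Model.** A linear model for each endpoint with implant group, age as a linear term and sex. Use one value per participant or, to keep the multi-level approach, daily values with a participant random effect and the same fixed terms. The two give the same group contrast when participants contribute equal numbers of valid days.
- **Reporting.** The adjusted RHA-THA difference with its 95% CI, and the crude difference beside it.
- **Covariates.** Fixed in advance, with no selection by significance. BMI, diagnoses and medication recorded after surgery stay out of this model, because they may be consequences of the implant or of activity. Section 12.1 does not date these records, so the dates should be stated.

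Separately, reconcile the 82 randomised with the 34 and 26 in section 8.2, and report how many in each group were reached, consented and were analysed.

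The cost is a short addition to the text and two degrees of freedom. No new data are needed. If age and sex turn out to explain very little, the adjusted interval may be slightly wider than the crude one, and both will be on view.

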SQUASH	Short Questionnaire to Assess health-enhancing physical activity
THA	Total Hip Arthroplasty
UCLA	University of California at Los Angeles
UK	United Kingdom
WMO	Medical Research Involving Human Subjects Act; in Dutch: Wet Medisch-wetenschappelijk Onderzoek met Mensen

SUMMARY

Rationale:

Arthritis significantly impacts patients' lives, affecting everything from pain and fatigue to daily activities and overall mortality. Physical activity (PA), particularly moderate-to-vigorous physical activity (MVPA), is crucial in managing arthritis symptoms and reducing mortality risks, with even minimal MVPA providing significant health benefits. Wearable technology has revolutionized the measurement of physical activity, offering accurate, large-scale data that informs treatment efficacy. Despite this, little is known about how common arthritis treatments affect physical activity levels, highlighting a critical gap in our understanding. Joint replacement, while effective in reducing pain and improving function, shows varying long-term mortality outcomes, suggesting the need for further research into how different surgical procedures impact patients' activity levels and overall well-being.

Objectives: i) To compare the volume and intensity of physical activity 15 years after surgery in patients after hip resurfacing and total hip replacement and ii) to explore the association between the participants' physical activity and functional outcome scores.

Study design: A cross-sectional observational (follow-up) study.

Study population: We will approach patients that have previously participated in a randomised controlled trial during which they received either hip resurfacing ($n = 34$) or total hip replacement ($n = 26$).

Intervention (if applicable): In this study there is no intervention, only observation using accelerometers. Participants will be asked to complete four physical activity questionnaires. Subsequently, they will wear a tri-alaxial accelerometer on their non-dominant wrist continuously for ten days and nights, and simultaneously wear a tri-axial accelerometer taped to the surgical thigh for a period of 48 hours.

Main study parameters/endpoints: Using the accelerometers we will measure the participants' physical activity energy expenditure (PAEE), the intensity distribution of PAEE and step count. Secondary outcomes include self-reported physical activity, health status and the ability to perform specific activities.

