1. INTRODUCTION AND RATIONALE

1.1 Arthritis and physical activity

The impact of arthritis is wide-ranging and patient specific. From traditional symptoms such as fatigue and pain to more holistic considerations like holiday destination and pragmatism over style(1), arthritis affects many patient life domains. Treatment strategies are similarly broad - spanning lifestyle changes, medicine, and surgery - as is the definition of what constitutes success in treatment. Surveys of arthritis sufferers have identified a reduction in fatigue, pain and a return to normal activities as core expectations of this patient group(1),(2), but again, answers are highly personal. Yet beyond commonly reported symptoms, some forms of arthritis are associated with a shortened life span. For example, a 15-year prospective study of rheumatoid arthritis patients in the Netherlands revealed significantly higher all-cause mortality in rheumatoid patients (3). Likewise, lower limb osteoarthritis is associated with increased cardiovascular mortality (4) and all-cause mortality (5). Further, gait speed, which commonly decreases with end-stage arthritis, independently predicts mortality in the elderly (6). Recent population-based studies suggest that a lack of physical activity may explain, at least in part, these findings. Physical activity researchers are ever more aware of the importance of physical activity volume and intensity in healthy ageing, both for all-cause mortality and intermediate disease states (7),(8),(9),(10),(11),(12). In a population-based study of over 96,000 participants, Strain et al. demonstrated that physical activity volume and intensity are independently associated with all-cause mortality (7). Figure 1 illustrates this relationship, but it also highlights the additional benefit of accumulating a greater fraction of physical activity energy expenditure (PAEE) from moderate-to-vigorous physical activity (MVPA).

[figure not shown]

Figure 1. PAEE, intensity and all-cause mortality (7).

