8. METHODS

8.1 Study parameters/endpoints

8.1.1 Main study parameter/endpoint

In order to gain insight into the volume and intensity of physical activity, both the wrist-worn GENEActiv triaxial accelerometer and the thigh-worn Axivity AX3 Logging tri-axial accelerometers will measure physical activity energy expenditure (PAEE) (7) and the intensity distribution of PAEE (7),(8). The wrist worn GENEActiv triaxial accelerometer will additionally measure the participants' step count (28),(35).

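### Section 10.1 states no resurfacing-versus-total-hip estimate for the primary objective, and does not fix the device or the intensity measure for that comparison.

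*Combined protocol and SAP*

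**What the plan says.** Section 2.1 gives the primary objective: "To compare the volume and intensity of physical activity 15 years after surgery in patients after hip resurfacing and total hip replacement".

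Section 8.1.1 assigns PAEE and its intensity distribution to both the wrist-worn and the thigh-worn accelerometer. Step count is assigned to the wrist device alone. Section 8.3.1 has the wrist device worn for ten days and nights and the thigh device for 48 hours.

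Section 10.1 describes the signal processing and the prediction models used "to calculate physical activity energy expenditure, time in moderate-to-vigorous physical activity, and step count". Its statistical content is then:

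- descriptive statistics, not said to be by procedure group;
- for the performance of multi-level linear regression models, "we will conduct ANOVA repeat measures analysis to calculate Pearson's coefficient and Root Mean Squared Error metrics";
- a check across patient subgroups, in these words: "Differential bias will be assessed by age, sex, and BMI categories".

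The multi-level models are mentioned only as objects whose validity and performance will be examined. Their outcome, covariates and levels are not given.

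Section 10.2 plans univariate and multivariate regression in relation to the questionnaire outcomes, with PAEE and patient characteristics as examples of the factors considered. It does not name procedure group.

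On intensity, the main parameters in the Summary include "the intensity distribution of PAEE and step count", and section 8.1.1 uses the same term for intensity. Section 10.1 instead derives time in moderate-to-vigorous activity (MVPA). The rationale in section 1.1 uses a third form, the fraction of PAEE that comes from MVPA.

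**The concern.** The stated primary method targets a different quantity from the primary objective. A correlation coefficient and a root mean squared error describe how well a model predicts. Differential bias by age, sex and BMI describes where its predictions go wrong. None of the three says how much more or less active one surgical group is than the other.

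If the contrast is left to be written later, so are the choices of device and intensity measure. The two devices cover different lengths of time, and the intensity measures are different quantities, so the choices can change the answer. In a cohort of at most 34 + 26 patients, choices made after the data are seen can follow the result, and a reader of the eventual paper could not tell.

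**Working it through.** **1. Objective against analysis.** The plan states no effect size, alpha, power or sample-size calculation, so there is no figure of its own to reproduce. The check is to set each analysis in section 10 against the quantity in section 2.1.

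| Analysis stated | Quantity produced | RHA minus THA difference? |
|---|---|---|
| Descriptives (10.1) | Means or medians, proportions; not said to be by group | No |
| Repeated-measures ANOVA (10.1) | Pearson's coefficient, RMSE | No |
| Differential bias (10.1) | Bias by age, sex, BMI category | No |
| Regression (10.2) | Factors related to questionnaire outcomes; procedure group not named | No |

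Number of RHA minus THA estimates specified: 0.

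**2. Candidate primary comparisons.** From section 8.1.1: PAEE on 2 devices + intensity on 2 devices + step count on the wrist = 2 + 2 + 1 = 5. If both intensity forms (the distribution in 8.1.1 and MVPA time in 10.1) are counted on each device: 2 + 4 + 1 = 7. The plan ranks none of them.

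**3. Recording time.** Wrist: 10 × 24 = 240 h. Thigh: 48 h. Ratio 240 / 48 = 5.

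**4. Can the intensity measures disagree?** Let one group spend energy L in light activity and M in MVPA, with T minutes in MVPA. Let the other do twice as much of everything: 2L, 2M, 2T. MVPA time doubles. The share of PAEE from MVPA is 2M / (2L + 2M) = M / (L + M), which is unchanged. So one measure shows a doubling and the other shows nothing. This holds only if the distribution is expressed as proportions. Energy per intensity band in absolute units would double too. Section 8.1.1 does not say which is meant.

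**5. Precision of the contrast once stated.** This is context and does not measure the defect. Unadjusted 95% CI half-width in SD units = t(0.975, n1 + n2 − 2) × √(1/n1 + 1/n2). Group sizes come from section 4. The documents give no participation rate, so the rates below are assumptions.

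| Participation | n1 + n2 | Calculation | Half-width |
|---|---|---|---|
| 100% | 34 + 26 | 2.0017 × 0.2605 | 0.52 SD |
| 80% | 27 + 21 | 2.0129 × 0.2910 | 0.59 SD |
| 50% | 17 + 13 | 2.0484 × 0.3684 | 0.75 SD |

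**6. Cost of adjusting for age and sex if they explain nothing.** Ratio = [t(n − 4) × adjusted SE] / [t(n − 2) × unadjusted SE] at the same residual SD, with n = n1 + n2. This was averaged over 40,000 simulated cohorts per setting, with one normal and one 50% binary covariate, neither related to outcome. Repeat runs agree to within about 0.2 percentage points on the means.

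| n1 + n2 | Covariates unrelated to group: mean (95th percentile) | Mean age differs by 0.5 SD: mean (95th percentile) |
|---|---|---|
| 34 + 26 | +1.9% (about 5.4%) | +5.0% (about 12%) |
| 17 + 13 | +4.2% (about 12.4%) | +7.6% (about 21%) |

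**The case against.** The strongest reply is that section 10.1 does refer to multi-level linear regression models, and one of these may have been meant to carry the group comparison. That is possible. A reader might therefore go too far in inferring that the sponsor intends no comparison. The documents support only the narrower statement that the comparison is not written down: the models have no stated outcome or group term, and their only stated use is a performance check.

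A sponsor may also point to section 10.2. Its regression does include patient characteristics, but it concerns questionnaire outcomes and does not name procedure group, so it does not fill the gap.

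Three further replies stand and limit the point.

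- Step count is tied to the wrist device, so the device question applies only to PAEE and intensity.
- Section 10.1 brings wrist and thigh data to a common time resolution, so a combined estimate may be intended. The plan need not choose a single device, but it should name the device or the combination.
- MVPA time may be meant as one summary of the intensity distribution. Sections 8.1.1 and 10.1 are then imprecise and not flatly contradictory. The measure used for the comparison is still not fixed.

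The half-widths above should not be read as the size of this fault. They reflect the number of patients, and better wording will not change them.

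**Conclusion.** The point holds and should be corrected before the data are analysed. The plan states the comparison as its primary objective, and section 10 specifies no estimate of it. The listed primary method measures model performance. For PAEE and intensity the primary data source is open between 240 hours and 48 hours of recording, and the intensity measure is worded differently in the endpoint and analysis sections.

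These conclusions rest on the text alone. Two things rest on assumptions: that the intensity measures can disagree (which needs a distribution expressed as proportions) and the precision figures (which need a participation rate).

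A separate, minor item concerns the population. Section 8.2 says "a total of 82 patients were randomly assigned to receive resurfacing hip arthroplasty" or conventional total hip replacement, but gives arms of 34 and 26. That is 34 + 26 = 60, leaving 82 − 60 = 22 (22 / 82 = 27%) unexplained. Section 8.2 then says all participants of that trial will be contacted, while section 4 describes the patients to approach as 34 and 26. A reader might infer that the groups are wrong or that patients were dropped. The documents do not show this: 34 and 26 are given consistently in the Summary and in sections 4 and 8.2, and the explanation may lie in the earlier trial's report.

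**What to change.** In section 10.1, state as the primary analysis:

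- The RHA minus THA difference with 95% CI for (a) mean daily PAEE and (b) one intensity measure, worded identically in 8.1.1 and 10.1. The share of PAEE from MVPA is one option, since the rationale in 1.1 uses it.
- The data source: one named device or a named combination. The ten-day wrist monitor is one option, as it records longer and section 1.2 calls it suitable after lower limb arthroplasty.
- The model: linear regression on procedure group with a short pre-stated covariate set, for example age and sex, with BMI in a sensitivity model. Alternatively, keep the multi-level model on daily data, with procedure group as a fixed effect and a participant random intercept, and report that coefficient with its CI.
- A pre-stated check or fallback for skewed outcomes.
- A commitment to report both results whatever they show, and not to read a CI that includes zero as no difference.

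Report step count and the other device's measures as secondary estimates. Keep Pearson's coefficient and RMSE only as a check of model performance.

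Separately, reconcile 82 with 34 + 26 in section 8.2, say who is contacted, and state whether groups are analysed as randomised or as received.

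Cost: no new data, since section 12.1 already has age, gender and BMI collected. It needs protocol wording (an amendment notified to the METC if approval has been given), a check of the earlier trial's allocation records, and commitment to the lead measures in advance. If age and sex explain nothing, the CI widens by about 2% on average at 34 + 26 and 4% at 17 + 13, and by more if age differs between the groups.

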3. STUDY DESIGN

This is a cross-sectional observational (follow-up) study in which we will ask participants to complete four paper questionnaires, wear a tri-axial accelerometer on their non-dominant wrist continuously for ten days and nights, and simultaneously wear a tri-axial accelerometers taped to the surgical thigh for a period of 48 hours.

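### A repeated-measures ANOVA does not directly give RMSE or Pearson's coefficient as a measure of model performance, and its residual can hide a mean shift between methods

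*Combined protocol and SAP*

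**What the plan says.** Section 10.1 summarises the accelerometer signal by minute ("The acceleration signal will be summarised to a common time resolution of one observation per minute") and applies models whose purpose is "to calculate physical activity energy expenditure, time in moderate-to-vigorous physical activity, and step count". It then turns to validation. The purpose of this step is given as follows: "To examine face validity and the performance of each multi-level linear regression model". The means chosen for it is a single named analysis, stated in these words: "we will conduct ANOVA repeat measures analysis to calculate Pearson's coefficient and Root Mean Squared Error metrics". Bias is also to be checked across age, sex and BMI groups, by a method that is not stated.

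The section does not give the outcome, predictors or levels of the multi-level models. It names no comparator for the predictions, no repeated unit and no error term. It states no expected RMSE or correlation and no limit of acceptability.

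The design in section 3 offers several possible repeated units. Participants are to "wear a tri-axial accelerometer on their non-dominant wrist continuously for ten days and nights" and a second device is "taped to the surgical thigh for a period of 48 hours", so the repeated factor could be the minute, the day or the device.

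The primary objective in section 2 is "To compare the volume and intensity of physical activity 15 years after surgery in patients after hip resurfacing and total hip replacement". Section 4 gives the pool: "These include 34 patients after hip resurfacing and 26 patients after total hip replacement", at most 34 + 26 = 60 people.

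**The concern.** A repeated-measures ANOVA splits the variation into a participant part, a part for the repeated factor, and a residual. The root of the residual mean square is often printed as root MSE, and the sentence in section 10.1 invites its use as the RMSE. That number describes scatter within a person after the participant's own level, and the average effect of the repeated factor, have been taken out. It is not the error of a prediction, nor of one device against another.

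Pearson's coefficient is not a standard output of this ANOVA at all. An analyst would have to choose what to correlate, and the choices give different answers.

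What is at stake is the statement about how well the activity estimates perform. The two surgical groups are different people, so a validity figure meant to support comparing them should include error that differs between people and should show any systematic shift.

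**Working it through.** The plan states no RMSE, correlation, intraclass correlation (ICC) or bias, so there is no figure to reproduce. Every ICC, SD, bias and correlation below is an assumption used to show direction and size.

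**Two methods per participant (method is the repeated factor).** Let the paired differences have mean *bias* and standard deviation SD_diff = 1.

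- ANOVA root MSE = SD_diff/√2 = 1/1.414 = 0.71, whatever the bias.
- RMSE of the differences = √(SD_diff² + bias²).

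| Bias | ANOVA root MSE | RMSE of differences | ANOVA × √2 | Shortfall after rescaling |
|---|---|---|---|---|
| 0 | 0.71 | √1.00 = 1.00 | 1.00 | 0% |
| 0.5 | 0.71 | √1.25 = 1.12 | 1.00 | 1 − 1/1.118 = 11% |
| 1.0 | 0.71 | √2.00 = 1.41 | 1.00 | 1 − 1/1.414 = 29% |

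The raw shortfall is 29% with no bias (1 − 0.707) and 50% at a bias of 1.0 (1 − 0.707/1.414). With no bias, the 29% only reflects that the SD of a difference is √2 times the error SD of a single measurement. Multiplying the ANOVA figure by √2 removes that part. What remains, 11% and 29%, is the mean shift that the ANOVA residual cannot show.

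**Repeated days per participant.** Take ten days, total variance 1, ICC ρ, and a model with no predictive information (an extreme case, chosen for clarity).

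- ANOVA residual SD = √(1 − ρ).
- Error for one day of a new person = 1.00 at every ρ.
- Error for the ten-day mean of a new person = √(ρ + (1 − ρ)/10), ignoring the small error in the overall mean.

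| ρ | ANOVA residual | New person, single day | New person, ten-day mean |
|---|---|---|---|
| 0.4 | √0.6 = 0.77 | 1.00 | √0.46 = 0.68 |
| 0.5 | √0.5 = 0.71 | 1.00 | √0.55 = 0.74 |
| 0.7 | √0.3 = 0.55 | 1.00 | √0.73 = 0.85 |

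Against single-day error the residual is smaller by the factor √(1 − ρ). Against error in one value per participant it is larger at ρ = 0.4 and smaller at 0.5 and 0.7. The two are equal when 0.9(1 − ρ) = ρ, that is ρ = 0.9/1.9 = 0.47.

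**Pearson's coefficient.** Simulations used 60 participants, ten days and ICC 0.5, with 300 runs per scenario.

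| Between-person r | Within-person r | Pooled r | r with participant means removed | Multiple R with participant terms |
|---|---|---|---|---|
| 0.8 | 0.8 | 0.80 | 0.80 | 0.91 |
| 0.8 | 0.4 | 0.60 | 0.40 | 0.78 |
| 0.4 | 0.8 | 0.60 | 0.80 | 0.91 |

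Removing participant means can leave r unchanged, lower it or raise it. Only the correlation of observed values with fitted values that contain participant terms is higher than the pooled r in all three cases. In the extreme case of a model with no predictive information, that correlation was 0.67, 0.74 and 0.85 at ICC 0.4, 0.5 and 0.7.

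**The case against.** The best defence is that section 10.1 does not say that RMSE will be the root of the ANOVA residual mean square, or that r will be taken from fitted values with participant terms. The authors may have used the ANOVA label loosely and intend ordinary metrics on paired values. This stands, and it makes the point conditional. It does not remove it: if the ANOVA is not the source of the metrics, the section does not define them at all.

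A second defence is that SD_diff/√2 is a legitimate within-person quantity, so a 29% gap with no bias is a change of scale and not an error. This also stands. It leaves the hidden shift untouched.

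A third is that bias is to be checked by age, sex and BMI. That check could reveal a shift if mean differences are tabulated, but the section does not say that they will be.

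A reader might infer three stronger things that the documents do not support:

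- *The reported error will always be too small.* At an ICC of 0.4 the residual (0.77) exceeds the error for one value per participant (0.68). The contrast with 1.00 concerns single days.
- *The correlation will always look too good.* That requires fitted values with participant terms, which the plan does not specify.
- *The comparison of resurfacing with total hip replacement is biased.* The sentence concerns model performance and does not specify that comparison.

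**Conclusion.** The point holds in a limited form. The named method does not directly yield RMSE or Pearson's coefficient as a measure of prediction or agreement. If RMSE is read from the ANOVA residual, it leaves out stable between-person error and, with method as the repeated factor, any mean shift. With SD_diff = 1, the true RMSE rises from 1.00 to 1.41 as bias goes from 0 to 1.0, and the ANOVA figure does not move. With repeated days the residual describes day-to-day error within a person, and its relation to person-level error depends on the ICC. The direction for Pearson's coefficient is not fixed unless participant terms enter the fitted values.

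The actual size cannot be computed from the documents. The consequence is confined to the validity claim for the activity estimates. The wording should be changed before analysis, because following it literally gives the wrong error figure and the better calculation is simple.

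**What to change.** Drop the ANOVA as the source of these metrics in section 10.1 and state instead:

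- the comparator for each predicted quantity, and the time window over which the two are paired;
- RMSE as the square root of the mean squared difference between prediction and comparator, with the mean shift kept in;
- one value per participant, with predictions from the fixed part of the multi-level model only;
- Pearson's coefficient computed on the same pairs, with the mean difference reported beside it.

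Leave-one-participant-out prediction, limits of agreement and participant-level bootstrap intervals are useful but optional in a study of at most 60 people.

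The cost is a few lines of text and code, with no new data. The stated performance may look less favourable.
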